6.5 CRITERIA FOR TREATMENT CONTINUATION

Further treatment cycles (i.e., Cycle 2 or subsequent) will be administered every q3wk (± 48 hours) if the patient fulfills all the re-treatment criteria defined in [Table 6](#).

Table 6. Criteria for treatment continuation.

Variable	Re-treatment (Day 1)
ECOG PS	≤ 2
Hemoglobin*	≥ 8.0 g/dl
ANC	≥ 1.5 × 10 ⁹ /l
Platelets	≥ 100 × 10 ⁹ /l
AST/ALT	≤ 3.0 × ULN
Total bilirubin or direct bilirubin	≤ 1.5 × ULN or × ULN
Albumin	≥ 3 g/dl
Serum creatinine	≤ 1.5 × ULN or creatinine clearance ≥ 30 ml/min
CPK	Grade ≤ 1
Other non-hematological drug-related AEs (except isolated increased GGT and/or AP; grade 2 asthenia, constipation, alopecia, peripheral neuropathy, or non-optimally treated nausea and/or vomiting)	Grade ≤ 1
Active infection (including sepsis) and/or bleeding (any grade)	Absence

* Patients may receive packed red blood cells (PRBC) transfusion and/or erythropoietin (EPO) treatment, if clinically indicated, to increase/maintain adequate hemoglobin levels.

AE(s), adverse event(s); ANC, absolute neutrophil count; AP, alkaline phosphatase; AST/ALT, aspartate aminotransferase/alanine aminotransferase; CPK, creatinine phosphokinase; ECOG, Eastern Cooperative Oncology Group; GGT, gamma-glutamyltransferase; PS, performance status; ULN, upper limit of

Variable	Re-treatment (Day 1)
----------	----------------------

normal.

If a patient does not meet the requirements for re-treatment on Day 1 of any following cycle, regardless of the reason, re-assessments will be performed at least every 48-72 hours. Treatment will be then withheld, up to a maximum of three weeks beyond its due date, until appropriate recovery.

Patients not meeting re-treatment criteria after a maximum 3-week delay must be withdrawn from trial. In case of objective clinical benefit, the patient could continue receiving the treatment (upon the Sponsors' agreement).

For any delay due to treatment-related adverse events lasting for more than one week, a dose reduction must be implemented upon recovery, following the rules explained in the next section (Section 6.6).

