- This exploratory analysis will be performed on prior available paraffin-embedded tumor tissue samples from consenting patients of any arm. This sub-study will include factors involved in DNA repair mechanisms (such as nucleotide excision repair, homologous recombination repair and mismatch repair) and other factors related to the mechanism of action of PM01183 or to the pathogenesis of the disease, and their expression will be analyzed at the mRNA or protein level by quantitative polymerase chain reaction (PCR) and immunohistochemistry (IHC), respectively; their polymorphisms and mutations might be also analyzed, if relevant. Their correlation with clinical response and outcome after treatment will be assessed.

Safety Profile:

- Clinical examinations.
- Clinical assessment of AEs and serious adverse events (SAEs).
- Changes in laboratory parameters (hematological and biochemical, including liver function tests).
- Reasons for treatment discontinuations.
- Reasons for dose reduction and treatment delays.

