8.4 Treatment Administration

Total cumulative dose, dose intensity and relative dose intensity, time on treatment, cycle delays and dose reductions will be described following standard tables detailed in Appendix I.

Total cumulative dose, expressed in mg, will be the sum of all the study drug doses from the first cycle until the last cycle, including the dose received in the last cycle.

Patients will be considered to be on-treatment for the duration of their treatment and for 30 days after the last treatment dose. If the patient starts any new antitumor therapy outside this clinical trial or dies within 30 days of the last treatment dose, the date of administration of this new therapy or the date of death will be considered the date of treatment discontinuation.

However, as a convention, the duration of the last cycle will be considered to be 21 days (instead of 30 days) for dose intensity calculation purposes.

Intended dose intensity is the planned dose per cycle divided by the planned number of weeks per cycle.

Absolute dose intensity is the actual cumulative dose divided by the number of weeks of treatment. Relative dose intensity (%) is the ratio of absolute dose intensity divided by the intended dose intensity.

The CRF item «Infusion delayed: yes/no» will be used to calculate the delayed cycles. For those cycles considered as delayed by the Investigator, the delay will be calculated as follows:

Delay: Date of actual drug administration – Date of previous drug administration – 21.

The infusion of the first cycle will be excluded from all calculations regarding cycle delays and modifications.

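### SAP 8.4 lets the investigator's tick alone decide which cycles count as delayed, with no threshold for ticking and no check against the recorded infusion dates

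*SAP*

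**What the plan says.** SAP 8.4 (Treatment Administration) makes the CRF item the selector: "The CRF item «Infusion delayed: yes/no» will be used to calculate the delayed cycles". The date calculation comes second and is limited to the ticked cycles: "For those cycles considered as delayed by the Investigator, the delay will be calculated as follows". The formula is "Delay: Date of actual drug administration – Date of previous drug administration – 21". The first cycle is excluded.

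These rules feed Tables 12.1.2.2 to 12.1.2.5 in SAP Appendix I: counts for any relationship, treatment-related counts, reasons, and length. Length is split into up to 7 days, over 7 and up to 14 days, and over 14 days. Listing 12.1.2.1 shows dates only for cycles already classed as delayed. Listing 14.1.20 carries the administration date for each visit beside a separate delayed yes/no item and its reason.

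Protocol 6.5 sets the schedule, "Further treatment cycles (i.e., Cycle 2 or subsequent) will be administered every q3wk", with a tolerance of 48 hours either way. It also gives delay length a consequence: "For any delay due to treatment-related adverse events lasting for more than one week, a dose reduction must be implemented upon recovery". The related safety endpoint in SAP 3.3 is worded "Reasons for dose reduction and treatment delays".

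**The concern.** Whether a cycle was late is a matter of dates, and the dates are collected. The SAP instead asks the investigator to decide, without stating a threshold. The 48-hour window in protocol 6.5 is not carried into SAP 8.4. Table 12.1.2.2 covers delays of any relationship, so no judgement about cause is needed to decide whether a delay occurred.

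Two misclassifications follow. A late cycle ticked no is lost, and an on-schedule cycle ticked yes is counted. Listing 12.1.2.1 cannot reveal the first kind, because it starts from the ticked cycles. At stake is the reliability of the descriptive account of how well the three-weekly schedule was delivered.

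**Working it through.** The plan states no figure for delays, so there is nothing to reproduce. The check applies the SAP's own rules to hypothetical dates.

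**Inputs.** Cycle length 21 days and delay = interval − 21 (SAP 8.4). Window of 48 hours, taken as 2 days (protocol 6.5). Length rows from Table 12.1.2.5. Starting dose 3.2 mg/m² (protocol 6.3). Last cycle set to 21 days for dose intensity (SAP 8.4).

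**Step 1: single cycles.** The comparison rule counts a delay when the interval exceeds 21 + 2 = 23 days.

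| Interval | Tick | SAP 8.4 as written | Date rule |
|---|---|---|---|
| 30 days | no | not counted | delayed, 30 − 21 = 9 days, middle row |
| 30 days | yes | delayed, 9 days, middle row | same |
| 22 days | yes | delayed, 22 − 21 = 1 day, shortest row | not delayed |
| 22 days | no | not counted | not delayed |
| 21 days | yes | delayed, 21 − 21 = 0 days, shortest row | not delayed |

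The shortest row has no lower bound, so even a computed delay of zero fits in it. Under the written rule the result changes with the tick at a fixed interval; under the date rule it does not.

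**Step 2: one patient, six cycles, constant dose.** There are five cycles that could be delayed.

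- All intervals 28 days: each delay is 28 − 21 = 7 days. SAP 8.4 gives 0 of 5 delayed if nothing is ticked and 5 of 5 if all are. The date rule gives 5 of 5.
- All intervals 23 days, inside the window: each computed delay is 2 days. SAP 8.4 gives 0 of 5 or 5 of 5 according to the tick. The date rule gives 0 of 5.

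**Step 3: dose intensity for the same patients.** "Absolute dose intensity is the actual cumulative dose divided by the number of weeks of treatment" and "Intended dose intensity is the planned dose per cycle divided by the planned number of weeks per cycle"; the tick enters neither. Intended intensity is 3.2/3 = 1.067 mg/m²/week.

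- 28-day intervals: weeks = (5 × 28 + 21)/7 = 23.0; absolute = 6 × 3.2/23.0 = 0.835; relative = 0.835/1.067 = 78.3%.
- 23-day intervals: weeks = (5 × 23 + 21)/7 = 19.43; absolute = 6 × 3.2/19.43 = 0.988; relative = 0.988/1.067 = 92.6%.

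Relative dose intensity is the same whichever box is ticked. In the 23-day case it is below 100% even though the date rule finds no delay, so agreement between the two measures should not be expected under either rule.

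**The case against.** The case for leaving the rule alone has real substance.

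- **Other capture routes.** A reader might infer that long delays are hidden and that adherence to the dose-reduction rule in protocol 6.5 cannot be checked. The documents do not support that. The rule concerns treatment-related adverse events. Listing 12.1.2.6 selects AEs whose recorded action was a delay, with the number of days, and Table 12.2.2.1 counts TEAEs leading to delay from the AE form; neither is stated to depend on the infusion tick. SAP 8.2 plans an analysis of deviations, including retreatment restrictions. Listing 14.1.20 shows tick, date and reason together, so a mismatch can be found line by line.
- **The endpoint.** It is tempting to call the delay rate a listed safety endpoint. The listed item is the reasons for delays, which only site entry can supply. Protocol 8.2.5 promises descriptive tabulation of delays and no more.
- **Conflict with dose intensity.** A reader might treat a low relative dose intensity beside zero delays as proof of error. It is not: dose reductions also lower dose intensity, and the 23-day example shows a gap that the date rule would leave in place.
- **Variation between sites.** That ticking differs by site is an inference from the missing definition. CRF guidance, edit checks in the data-entry system (SAP 9), monitoring (protocol 9.2) or the separate conventions document (SAP 8.15) might control it. None of that detail is in the protocol or SAP.
- **The 48-hour window.** It governs administration; neither document makes it a definition of delay.

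These arguments limit the consequences. They do not answer the core point: the tables are built on the tick, the tick is undefined in both documents, and no reconciliation with the dates is planned.

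**Conclusion.** The point holds as a modest improvement to descriptive exposure and safety tables. As written, SAP 8.4 can give different delay counts for identical dosing dates in Tables 12.1.2.2 to 12.1.2.5. It does not affect ORR or any hypothesis test.

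No magnitude can be given. The documents contain neither the share of late cycles nor how often sites would tick them, and the patients in the working are hypothetical. The one related remark, in protocol 1.10.1.3, is that neutropenia in the phase I experience rarely caused delays. It concerns one cause and says nothing about ticking accuracy.

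The conclusion assumes that no CRF guideline, edit check or conventions document outside the protocol and SAP defines the item or reconciles it with the dates. If one does, the remaining need is to state that definition in SAP 8.4.

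**What to change.** In SAP 8.4, for analysis counting only and without changing any dosing rule:

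1. Class every cycle after the first as delayed when the interval from the previous infusion exceeds 21 days plus the protocol's 48-hour window (more than 23 days). Set the length to the interval minus 21.
2. Use the CRF item and reason field to classify cause, adding a category for reason not recorded.
3. Build Tables 12.1.2.2 to 12.1.2.5 on this definition.
4. Add a listing of cycles where tick and dates disagree.

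The cost is a short SAP edit and minor reprogramming on data already collected. Short administrative delays that sites did not flag will now appear, so the reported rate may rise. Unticked late cycles will often have no recorded reason, so the treatment-related outputs (Tables 12.1.2.3 and 12.1.2.4) may change little; the gain is mainly in Tables 12.1.2.2 and 12.1.2.5.

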8.5 Subsequent Therapy

A table summarizing the subsequent therapies received after treatment discontinuation will be shown.

8.6 Pharmacokinetic Analyses

This analysis will be detailed in a separate document.

8.7 Pharmacogenetics Analyses

This analysis will be detailed in a separate document.

8.8 Pharmacogenomic Analyses

This analysis will be detailed in a separate document.

8.9 Imputation of Incomplete Dates

The dates of certain historical or on-study clinical data are key components for statistical analysis. An incomplete date results from a missing day, month or year; in that case, the missing figure can be imputed, thus allowing the calculation of variables, such as duration and time of a specific event. However, when all dates (day, month and year) are missing, no imputation will be done unless otherwise specified. Whenever imputations are applicable, it will be clearly specified in the corresponding shell table, listing or figure in sections 10-16 of this SAP.

Before Registration

If the day of a month is unknown, then the imputed day will be the 1st. of the month; if the month is also unknown, then the imputed date will be the 1st of July. This assumption will only be valid if the imputed date occurs earlier than the first dose administration date; otherwise the imputed date will be the first day of the month of administration of the first dose (i.e. 01/ month of administration of the first dose/year).

Between treatment start and end of treatment

All date variables during treatment where information is needed and is not fully available, for example adverse events or concomitant medications, will be subject of imputation by means of SAS programming. If the day of a date is unknown then the imputed day will be 1, if the month and/or year is also unknown then the imputed date will 1/January (this assumption will be valid if the imputed date is later than the treatment start date; otherwise, the imputed date will be the treatment start date).

After End of Treatment

To ensure the most conservative approach for the time-to-event variables (i.e., DR, PFS and OS), which can be affected by missing values, the following rules will be implemented: if the day of a date is unknown then the imputed day will be the 1st; if the month is also unknown, then the imputed date will be the 1st of July. This assumption will be valid if the imputed date occurs later than the last drug administration date; otherwise the imputed date will be the date of the last drug administration plus the predefined cycle length (i.e., 21 days if PM01183), except if the patient dies before, in which case the date of death minus 1 will be used. For OS, if a patient dies the imputation event date should be the last date the patient is known to be alive minus one day.

For the determination of treatment emergent AEs with incomplete dates that do not allow to know if they occurred during the treatment period, the following imputation rules will apply:

- If the start day, month and year are missing, the event will be considered treatment emergent.
- If the start day and month are missing, no date imputation will be performed but the event will be considered TEAE, if the reported year is the same or occurs after the infusion year and also the reported year is the same or occurs before the EOT year.
- If the start day is missing, no imputation date will be performed but the event will be considered TEAE, if the reported month and year occur after the first infusion date (month/year) and before the EOT date (month/year).

-

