 - a) At least three weeks since the last chemotherapy (six weeks if therapy contained nitrosureas or systemic mitomycin C).
 - b) At least four weeks since the last monoclonal antibody (MAb)-containing therapy, or radiotherapy (RT) > 30 gray (Gy).
 - c) At least two weeks since the last biological/investigational therapy (excluding MAbs) or palliative RT (≤ 10 fractions or ≤ 30 Gy total dose).
 - 9) Grade ≤ 1 toxicity due to any previous cancer therapy according to the NCI-CTCAE, v.4. Grade 2 is allowed in case of alopecia and/or peripheral sensory neuropathy.
 - 10) Women of childbearing potential must have pregnancy excluded by appropriate testing before study entry. Fertile women must agree to use a medically acceptable method of contraception throughout the treatment period and for at least three months after treatment discontinuation. Fertile men must agree to refrain from fathering a child or donating sperm during the trial and for four months after the last infusion.

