8.11 Subgroup Analyses

Specific subgroup efficacy analyses will be done for patients with SCLC. These analyses will be performed by IA/IRC and in all evaluable/all treated patient populations, pre-specified analyses are by CTFI defined as the time from the last dose of the last platinum containing therapy to the occurrence of progressive disease,(< 90 days and \geq 90 days and/or Refractory (RR) [$<$ 30 days], Resistant (R)[\geq 30 and $<$ 90 days], Sensitive (S) [\geq 90 and $<$ 180 days] and Very Sensitive (VS)[\geq 180 days]), excluding patients with CTFI $<$ 30 days and considering event to clinical progressions although they

were not documented by radiological images. Any other exploratory analyses requested by the physician at the time of the analysis will be clearly explained, specifying the selected patient population and following the same layout detailed for the other subgroup analyses.

If the number of patients recruited in any cohort differs at least 10% from the sample size assumptions, a sensitivity analysis for main efficacy endpoints using all evaluable patients will be performed.

Pre-specified safety subgroup analyses are: by sex (male vs. female), by age (<65 years-old vs. ≥65 years-old), by race (white vs. other), by number of prior lines (1 vs. >1 line), by BSA (<1.8 vs. ≥1.8) and by geographical area (USA vs. Europe vs. rest of the world).

No differentiation by center is planned.

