11.1.13 Prior Anticancer Therapy

Each table, listing and figure displayed in this section will have a comprehensive header identifying the tumor type (cohort) or the total population (if applicable).

Table 11.1.13.1 Patients with prior surgery.

	N	%
Yes	X	X.X
Palliative		
Curative		
No		
Total		

Table 11.1.13.2 Patients with prior radiotherapy

	N	%
Yes		
Brachytherapy	X	X.X
External (including IMRT)	X	X.X
IMRT		

No		
Total		

Table 11.1.13.3 Number of lines of prior therapy.

No. of systemic lines	N	%
1	X	XX.X
...		
Total		
Mean, Standard Deviation, Median (Range)		
Setting	N	%
Neoadjuvant	X	XX.X
Adjuvant		
Neoadjuvant + Adjuvant		
Advanced		
No. of advanced chemotherapy lines	N	%
1	X	XX.X
...		
Total		
Mean, Standard Deviation, Median (Range)		

Note: Also for s1 and s2.

Table 11.1.13.4 Prior anticancer agents.

Antineoplastic and immunomodulating agents (ATC-class.)	N	%
Antineoplastic agents (L01)	X	XX.X
Alkylating agents		
Nitrogen mustard analogues		
Alkyl sulphonates		
Prior anticancer agents*		
Hormones		
Prior Immunotherapy		
...		
Biological agents		
...		
.....		

Note: Also for s1 and s2; (*) Therapies of interest for each tumor type e.g MBC, endometrial carcinoma, hormone, Biological agents etc.....

Table 11.1.13.5 PCI.

*	N	%
Yes	X	XX.X
No		
Total		

Note: Also for s1 and s2; (*) Only for SCLC patients.

Table 11.1.13.6 CTFI by subgroup.

*	N	%	Mean, Std., Median, Range**
CTFI < 90 days	X	XX.X	
RR			
R			
CTFI ≥ 90 days			
S			
VS			
Total			

(*) Only for SCLC patients. (**) Units in months.

Table 11.1.13.7 Best response and TTP to last prior platinum.

*	N	%
CR	X	XX.X
PR		
SD		
PD		
UK/NA		
Total		
TTP to last previous platinum Mean, Std., Median, Range		

(*) Only for SCLC patients. Note: Also for s1 and s2.

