11.3 Efficacy Analysis

Efficacy analysis will be carried out on the “All Evaluable Patients” population. For SCLC patients in “All Treated Patients” and in “All Evaluable Patients” by IA/IRC and in all pre-specified analyses, by CTFI (< 90 days and ≥ 90 days and/or Refractory (RR)[<30 days], Resistant (R) [≥30 and <90 days], Sensitive (S) [≥90 and <180 days] and Very Sensitive (VS) [≥180 days]), excluding patients with

CTFI<30 days and considering event in the clinical progressions although they were not documented by radiological images.

Each table, listing and figure displayed in this section will have a comprehensive header identifying the tumor type (cohort), the total population (if applicable) or SCLC patients by CTFI or sensitivity analysis if recruitment in any cohort differs at least 10% from the assumptions. Any other exploratory analyses will be clearly specified by selected patient population and will be performed following the same table layout detailed below.

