			VS			
			Total			
Disease control rate**	IA	CTFI < 90 days	RR			
			R			
			Total			
		CTFI ≥ 90 days	S			
			VS			
			Total			
	IRC	CTFI < 90 days	RR			
			R			
			Total			
		CTFI ≥ 90 days	S			
			VS			
			Total			

(*) CR + PR + SD ≥ 4 months. Binomial exact estimator and 95% CI.

(**) CR + PR + SD. Binomial exact estimator and 95% CI.

Table 11.3.3.25 PFS IA by CTFI (All treated patients).

	CTFI < 90 days*			CTFI ≥ 90 days*		
	RR**	R**	Total*	S**	VS**	Total*
N						
Events						
Censored						
Median PFS						
PFS at 4 months						
PFS at 6 months						
PFS at 12 months						

(*/**) Kaplan-Meier plots will also be shown. (*) Table/Figure 11.3.3.25.1 with the following categories (CTFI < 90 days and CTFI ≥ 90 days), (**) Table/Figure 11.3.3.25.2 with the following categories RR, R, S and VS.

Table 11.3.3.26 PFS IRC by CTFI (All treated patients).

	CTFI < 90 days*			CTFI ≥ 90 days*		
	RR**	R**	Total*	S**	VS**	Total*
N						
Events						
Censored						
Median PFS						
PFS at 4 months						
PFS at 6 months						
PFS at 12 months						

(***) Kaplan-Meier plots will also be shown. (*)Table/Figure 11.3.3.26.1 with the following categories (CTFI < 90 days and CTFI ≥ 90 days), (**) Table/Figure 11.3.3.26.2 with the following categories RR, R, S and VS.

Table 11.3.3.27 OS by CTFI (All treated patients).

	CTFI < 90 days*			CTFI ≥ 90 days*		
	R**	RR**	Total*	S**	VS**	Total*
N						
Events						
Censored						
Median OS						
OS at 6 months						
OS at 12 months						
OS at 24 months						

(***) Kaplan-Meier plots will also be shown. (*)Table/Figure 11.3.3.27.1 with the following categories (CTFI < 90 days and CTFI ≥ 90 days), (**) Table/Figure 11.3.3.27.2 with the following categories RR, R, S and VS.

Subgroup Analysis excluding CTFI < 30 days:

Table 11.3.3.28 Response rate IA and IRC excluding CTFI < 30 (All treated patients).

Response		N	%
IA	Complete response (CR)		
	Partial response (PR)		
	Stable disease SD ≥ 4 months		
	Stable disease SD < 4 months		
	Progressive disease (PD)		
	Inevaluable for response*		
IRC	Complete response (CR)		
	Partial response (PR)		
	Stable disease SD ≥ 4 months		
	Stable disease SD < 4 months		
	Progressive disease (PD)		
	Inevaluable for response*		

(*) for example: early death, malignant disease; toxicity; tumor assessments not repeated/incomplete; other (specify).

Table 11.3.3.29 ORR IA and IRC excluding CTFI < 30 (All treated patients).

Response rate*	Percentage	Lower 95% limit	Upper 95% limit
IA			
IRC			

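### When only the day of the last platinum dose is missing, imputing the 1st of the month lengthens CTFI by 0–30 days and can only move SCLC patients into a more sensitive class (minor; subgroup outputs only)

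*SAP*

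**What the plan says.** SAP 8.9, under Before Registration, has one rule for every historical date that lacks a day: "If the day of a month is unknown, then the imputed day will be the 1st". Its only safeguard concerns the first infusion: "This assumption will only be valid if the imputed date occurs earlier than the first dose administration date". Otherwise the date becomes the first day of the month of the first dose.

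SAP 8.11 gives CTFI as the pre-specified SCLC subgroup factor, "defined as the time from the last dose of the last platinum containing therapy to the occurrence of progressive disease". SAP 11.3 repeats the classes, beginning "Refractory (RR)[<30 days], Resistant (R) [≥30 and <90 days", followed by sensitive (90 to under 180 days) and very sensitive (180 days or more). SAP 11.3.3 adds a separate block of tables headed "Subgroup Analysis excluding CTFI < 30 days".

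Both ends of the interval are historical dates; Listing 14.1.9 (prior medical therapy) carries a stop date and a progression date. The SAP has no separate date rule for CTFI. On imputation generally, SAP 8.9 says that "it will be clearly specified in the corresponding shell table, listing or figure in sections 10-16 of this SAP", but the shell "Table 11.1.13.6 CTFI by subgroup" has footnotes only on cohort and units.

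**The concern.** Moving a start date to the first of its month can only move it earlier. Applied to the last platinum dose, with a complete progression date, this can only lengthen CTFI. The largest possible error, 30 days, equals the full width of the refractory class.

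CTFI defines the subgroup efficacy tables (11.3.3.18–27 and 11.3.3.36–37), the tables excluding CTFI under 30 days (11.3.3.28–33 and 11.3.3.38) and the resistant/sensitive outputs (s1/s2 in Appendix I). Protocol 1.1 says that patients with sensitive disease are much more likely to respond to further treatment. A one-directional shift therefore puts patients with a poorer outlook into the sensitive classes and leaves refractory patients in an analysis designed to drop them. As the shells stand, a reader of the tables could not see that this had happened.

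**Working it through.** The plan states no figure for this point, so there is none to reproduce. The check follows the date rule through to the classes.

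**1. Size and direction of the error.** With the progression date complete, computed CTFI − true CTFI = true day of month of the last platinum dose − 1. This lies between 0 and 30 days. Averaged over every calendar day of three years it is 14.73 days.

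**2. The safeguard does not help.** The 1st of the platinum month is never later than the true platinum date. Protocol 4.1 requires a washout: "At least three weeks since the last chemotherapy". The imputed date therefore always precedes the first infusion, and the fallback is never triggered.

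**3. Two examples.**
- Platinum 31 March 2016, progression 1 April 2016: true CTFI 1 day (refractory), computed 31 (resistant).
- Platinum 31 January 2016, progression 20 April 2016: true CTFI 80 days (resistant), computed 110 (sensitive).

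**4. Share changing class, true CTFI uniform over 0–364 days (assumption).** A shift of e days moves up only patients within e days below a cut. The expected share of a class crossing its upper cut is therefore mean shift ÷ class width:
- refractory to 30 days or more: 14.73/30 = 49%
- resistant to 90 days or more: 14.73/60 = 25%
- sensitive to 180 days or more: 14.73/90 = 16%
- all patients: 3 × 14.73/365 = 12.1% up, 0% down

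Full enumeration gives the same values.

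**5. Other missing-day patterns, same uniform assumption.**

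| Imputed | Error (days) | Mean | Up | Down | Refractory classed ≥30 |
|---|---|---|---|---|---|
| Platinum only, to the 1st | 0 to +30 | +14.7 | 12.1% | 0% | 49% |
| Progression only, to the 1st | −30 to 0 | −14.7 | 0% | 12.1% | 0% |
| Both, to the 1st | −30 to +30 | 0.0 | 10.4% | 0.6% | 44% |
| Platinum only, to the 15th | −14 to +16 | +0.7 | 3.4% | 2.8% | 14% |

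**6. A second shape for CTFI.** I simulated 400,000 patients with exponential CTFI, median 90 or 120 days (assumption), and only the platinum day missing:
- 1st of the month: 19% (median 90) or 16% (median 120) in the wrong one of four classes, all upward; 47–48% of the truly refractory reach 30 days.
- 15th, not allowed past progression: 9% or 8% in the wrong class; 13% of the truly refractory reach 30 days.

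If instead only the progression day is missing and set to the 1st, 8–10% of intervals come out negative. SAP 8.9 has no bound that prevents this.

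**7. Patient counts.** The number of month-only dates is not in the documents. Taking 10–30 of 100 SCLC patients as an assumed range:
- 1st: 10 × 0.16 = 1.6 to 30 × 0.19 = 5.7, about 2–6 misclassified
- 15th: 10 × 0.08 = 0.8 to 30 × 0.09 = 2.7, about 1–3 misclassified

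**The case against.** The strongest reply is that the practical effect is small and may be nil.

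- **Counts.** The 10–30 per 100 is an assumption; if every platinum date is complete, nothing changes. SCLC patients have one prior chemotherapy-containing line, and the washout check needs the date of last chemotherapy. Refractory patients, whose last dose may be close to entry, could be the least likely to lack a day. This stands as a limit on size, although it is an inference about data capture.
- **The 47–49% figure.** It applies only to refractory patients whose platinum day is missing. At 10–30% missing, unrelated to CTFI, it is 0.10 × 47% to 0.30 × 47%, about 5–14% of all refractory patients.
- **The main cut.** At 90 days alone, the exponential model misplaces 5–6% of affected patients with the 1st and about 3% with the 15th. With 10–30 affected, that is roughly 0.5–2 patients against 0.3–1.
- **Consequence.** The CTFI tables are descriptive and carry no test. Diluting the sensitive group would, if anything, work against the drug there. No effect on a subgroup response rate can be calculated from the documents.
- **Governance.** SAP 8.15 sends some conventions to a separate document. It defers only what the SAP does not already contain, and date imputation is contained, so the general wording of 8.9 covers these dates unless a CTFI rule is written.

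A reader might infer that the rule always favours more sensitive classes. The documents do not support that: the same sentence applied to a month-only progression date shortens CTFI. Nor do they support reading this as a threat to the primary SCLC result, which SAP 6.1 bases on all treated patients without a CTFI split.

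**Conclusion.** The point holds in a limited form and is minor. With only the platinum day missing and progression fully dated, the stated rule gives a biased CTFI (0 to +30 days, mean about 14.7) and can only move patients upward in class. That part is arithmetic. The share of such patients who are refractory but classed at 30 days or more is roughly half under both CTFI shapes tried.

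With only the progression day missing, the bias has the opposite sign and can produce negative intervals. With both missing, the mean error is about zero but upward moves still dominate. If the month is also missing, 1 July applies and the error can go either way; that case is not sized here.

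The patient counts (about 2–6 against 1–3 per 100) depend on the assumed number of month-only dates and on the assumed CTFI distribution. The affected outputs are the CTFI subgroup tables, the s1/s2 outputs and the tables excluding CTFI under 30 days.

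**What to change.** Add a CTFI-specific rule to SAP 8.9 or 8.11 and leave the other historical dates as they are. Changing the general sentence would alter time since diagnosis, time since advanced disease and similar variables in all nine cohorts.

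1. When only the day of the last platinum dose or of progression is missing, impute the 15th, bounded so that last platinum dose ≤ progression ≤ first infusion.
2. Flag each SCLC patient whose CTFI class differs between the earliest and latest possible dates. This step is needed when both days are missing: moving both dates to the 15th gives the same interval as moving both to the 1st, so the mid-month value brings no gain there.
3. Repeat Tables 11.3.3.19 and 11.3.3.29 with the flagged patients classified at each extreme. Keeping them in avoids a selective exclusion.
4. Note the imputation, and the number of patients affected, on Table 11.1.13.6, as SAP 8.9 already promises for shells.

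The cost is a small derivation change, a footnote and two extra sensitivity tables. If no SCLC patient has a month-only date, the footnote says so and the extra tables are not needed.
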